5.1 Treatment Regimen

5.1.1 Treatment Regimen

The investigational drug is IBI308, given at the dose of 200mg IV Q3W up to 24 months until PD, death, intolerable toxicity, withdrawal of ICF, or other reasons stated in the protocol. Other drugs used in this study are non- investigational drugs.

5.1.2 Continuing Treatment After PD

During the treatment with IBI308, if subjects must meet all of the following criteria, he/she could continue to receive IBI308 after initial PD (first PD):

1. The investigator believes that continuing treatment may yield clinical benefits, and the disease is not progressing rapidly;
2. Subjects are able to tolerate investigational drug;
3. Stable ECOG PS score;
4. The treatment of serious complications requiring urgent interventions (such as CNS metastasis) could be managed on time;
5. Before continuing treatment with IBI308, subjects must be fully informed and the investigator must elucidate the foreseeable risks or discomforts and alternative treatments.

If the above criteria are met, the investigator and sponsor's medical manager will decide whether the subjects shall continue the treatment after PD, and document in the study records.

Data from subjects who continue IBI308 treatment after initial PD shall be collected. Refer to Table 1 for collection of data variables.

If the subjects continue to receive the investigational drug, imaging evaluation shall also be continued at the specified interval. Treatment is continued up to 24 months until further PD, death, intolerable toxicity, withdrawal of ICF, or other reasons stated in the protocol.

For subjects who continue IBI308 treatment after initial PD, treatment shall be discontinued if clinical symptoms worsen, even if there are no imaging evidence of further PD. It should be documented as "exacerbation of clinical symptoms".

5.2 Investigational Drug (IBI308)

5.2.1 Description

The investigational drug is a recombinant fully human anti-PD-1 monoclonal antibody injection, IBI308.

The main active ingredient of IBI308 is the recombinant fully human anti-PD-1 monoclonal antibody. The strength of IBI308 is 10 ml: 100 mg. IBI308 does not contain any preservatives. The concentration is 10 mg/mL, with excipients including 140 mmol/L mannitol, 25 mmol/L histidine, 20 mmol/L dihydrate sodium citrate, 50 mmol/L sodium chloride, 0.02 mmol/L disodium edetate (ethylenediaminetetraacetic acid disodium salt), and 0.2 mg/mL polysorbate 80, pH 6.0.

This product is a clear, colorless liquid, no foreign matter, flocs, and precipitation.

Manufactured by: Innovent Biologics (Suzhou) Co., Ltd..

5.2.2 Labels

The smallest packaging unit is a box. Each box contains two vials of IBI308 injection. The package label should contain the drug name, medication number, dosage form, strengths, drug code, batch number, expiration date, storage conditions, dosage and administration, precautions, and sponsor's information. The label on the vial contains the same information as the outer package except for dosage form and precautions. The package and vial shall be both labeled "use for clinical study only".

5.2.3 Storage

Store at 2–8°C away from light. The shelf life is 24 months. If quality issues such as turbidity and precipitation are observed in the injection, seal the vial immediately and notify the sponsor.

5.2.4 Preparation and administration

The preparation and administration of IBI308 is as follows:

1. Completely draw the contents of two vials of IBI308 injection and transfer them into a 100-mL IV infusion bag containing 0.9% (w/v) sterile sodium chloride solution, then document the start time of the preparation.

2. Gently invert the infusion bag to mix the solution, ensuring the uniformity of the contents. Do not violent shake t to avoid foam.

3. Administer with a 0.2–1.2 µm in-line filter (suggested infusion time is around 30~60 min). Document the start and stop time of infusion.

Note: For each dose infusions, do not mix the drugs of different batches; make sure that the IBI308 injection is clear without any quality issues such as turbidity or precipitation. Make sure that the time from drawing IBI308 from the first vial to the end of infusion is no more than 24 hours (storage conditions for the prepared solution is at 2 - 8 °C in the fridge or at the room temperature/under the light). Avoid mixing with other drugs. Do not administer as an IV bolus.

5.3 Administration Adjustments of Investigational Drug

5.3.1 General principles

- The subject's hematologic, hepatic, and renal function must meet the requirements for administration of study treatment prior to each dose. All the toxicities must resolve to NCI CTCAE v4.03 grade 0–1 or baseline levels (excluding alopecia, fatigue, etc.).
- Reasons for administration adjustments and actual changes shall be documented in the original medical records and electronic case report forms (Electronic case report form , eCRFs).

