4.4 Treatment Discontinuation/Withdrawal from the study

Subjects should discontinue treatment/withdrawal from the study in any of the following circumstances:

1. Subjects do not meet the inclusion/exclusion criteria, and are deemed unsuitable to continue in this study by the sponsor and investigator.
2. Subjects seriously violate the study protocol, and deemed unsuitable to continue in this study by the sponsor and investigator.
3. Subjects are enrolled in another clinical trial that is considered scientifically or medically incompatible with this study.
4. Subjects are lost to follow-up (study site personnel shall regain contact with the subjects to determine the cause of loss to follow-up and reschedule study visits if possible. The date and method of contact shall be documented in the study documents).
5. Decided by the investigator
 - Subjects should discontinue the treatment or withdraw from the study based on the safety and benefits of the subjects.
 - If the subjects require treatment with another drug for any reason, and the drug has been demonstrated to be effective for the indication of this study, then the subject shall withdraw from this study prior to starting the new drug.
 - PD is developed or the investigator believes that continuing with study treatment is not appropriate.
 - A life-threatening event that is treatment-related occurred, regardless of the severity of the event.
 - The investigational drug shall be discontinued due to toxicities (see Section 5.4).
6. Subjects or their representatives (such as parents or legal guardians) requests to withdrawal from the study or discontinue the investigational drug (subjects may be

eligible for long-term follow-up if he/she withdraws ICF for treatment but not for follow-up).

7. The sponsor may terminate the study or discontinue a subject from participating in the study due to medical, safety, regulatory, or other reasons related to the applicable laws, regulations, and Good Clinical Practice (GCP).
8. Subjects who delay the treatment for 6 weeks due to adverse reactions shall withdraw from the study.
9. Subjects may withdraw from the study if the investigator believes that the local lesions should also be treated with radiation or other therapies after the subject reaches the primary endpoint.

The reasons and dates of discontinuation for all the subjects shall be documented. Subjects who discontinue the treatment shall undergo other study procedures as specified in the schedule of visits.

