7.3 AE Severity Grading Scale

The severity of AEs is evaluated using the 5-level criteria of NCI CTCAE v4.03.

For adverse event terms not included in NCI CTCAE version 4.03, graded according to the following CTCAE classification principles:

- Grade 1 Mild; asymptomatic or mild signs; clinical or diagnostic observations only; medical intervention not indicated.

- Grade 2 Moderate; minimal, local or non-invasive intervention required; limiting age-appropriate instrumental activities of daily living (e.g., cooking, shopping, using the telephone and managing money, etc.).
- Grade 3 Severe or medically significant but not immediately life-threatening; hospitalization or prolonged hospitalization indicated; disabling; limiting self-care activities of daily life (e.g. bathing, dressing and undressing, feeding self, using the toilet, and taking medications), but not bedridden.
- Grade 4 Life-threatening consequences; urgent intervention indicated.
- Grade 5 Death related to AE.

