Appendix 7: IBI308 Administration Adjustments and Toxicity Management

Table 1. IBI308 administration adjustments and toxicity management of major potential irAEs

	AE Grade/Administration Adjustments		Toxicity Management
General Principles	AEs are graded according to NCI CTCAE v4.03. Refer to this guideline if the event is an irAE		
It is recommended to manage irAEs according to the guideline in this table.
 
 - Subjects shall be fully evaluated to rule out any alternative causes (e.g. PD, concomitant medication, infection, etc.) - The event is an irAE if there are no clear alternative causes and treatment with corticosteroids is required - Consider symptomatic and local treatment for low grade events (grade 1 or 2, unless otherwise stated) - Consider systemic glucocorticoid therapy for persistent low grade events (grades 1–2) or severe events (grade \geq 3) - If the event re-occurs or worsens during tapering of glucocorticoids, the glucocorticoid dose shall be increased until symptoms resolve
	Grade 1	No dose adjustments required	
	Grade 2	Interrupt 
 • If worsens, treat as a grade 3/4 event • If reduces to grades 0–1 or baseline, continue the treatment at the next scheduled date 	
	Grade 3	Interrupt or permanently discontinue	

	AE Grade/Administration Adjustments		Toxicity Management
	Grade 4	Permanently discontinue	
or improve, then taper with a lower rate
 
 - Once persistent clinical improvement is observed, subjects receiving glucocorticoids IV can start tapering the dose or switch to an equivalent dose of glucocorticoid PO at an earlier time (a lower bioavailability of oral administration should be considered) - For events that unresponsive to glucocorticoid treatment, consider a stronger immunosuppressants, e.g. TNF blockers (e.g. infliximab) or mycophenolate mofetil, after discussing with the physicians - For grade 3/4 local inflammation of lesions (such as local pain, irritation, and rash), IBI308 may be continued as determined by the investigator

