Hyperthyroidism/Hypothyroidism	Any grade		
 – Monitor signs and symptoms of thyroid dysfunction, e.g. hyperthyroidism (palpitations, sweating, increased appetite and bowel movement, and weight loss) and hypothyroidism (general weakness, fatigue, cold, memory loss, and constipation) – Subjects shall be fully evaluated to rule out any alternative causes – Monitor and evaluate thyroid function – Consider consulting an endocrinologist – Consider testing for thyroid autoantibodies (antithyroglobulin antibodies, anti-thyroid peroxidase antibodies, and thyroid-stimulating hormone receptor antibodies)

	AE Grade/Administration Adjustments		Toxicity Management
	Grade 1 or grade 2	No dose adjustments required	For grade 1–2 events: 
 – Monitor thyroid function and thyroid autoantibodies regularly – L-thyroxine replacement therapy or anti-thyroid medications when necessary
	Grade 3 or grade 4	Hyperthyroidism 
 • Permanently discontinue Hypothyroidism 
 • No dose adjustments • required 	For grade 3–4 events: 
 – Discuss with sponsor's medical manager – Monitor thyroid function and thyroid autoantibodies – Consult an endocrinologist Hyperthyroidism 
 – Anti-thyroid medications – Consider β-blockers for tachycardia Hypothyroidism 
 – L-thyroxine replacement therapy
Type I Diabetes	Any grade		
 – Monitor signs and symptoms closely, e.g. polyuria, polydipsia, polyphagia, fatigue, weakness, and weight loss – Subjects shall be fully evaluated to rule out any alternative causes – Monitor and assess pancreas islet function: blood glucose, insulin, c-peptide, β-cell autoantibodies, blood ketones, and other endocrine laboratory parameters related to type I diabetes
	Grade 1 or grade 2	No dose adjustments required	For grade 1–2 events: 
 – Monitor and assess pancreas islet function – Start insulin therapy when necessary

	AE Grade/Administration Adjustments		Toxicity Management

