	Grade 3 or grade 4	Permanently discontinue	
Myasthenia Gravis
 
 – Glucocorticoids may be used to treat myasthenia gravis (shall be used under the supervision of a neurologist since corticosteroids, especially high-dose, may result in initial exacerbation of symptoms) – Subjects intolerant to glucocorticoids may be treated with plasmapheresis or IVIgG – For myasthenia gravis-like neurotoxicities, consider acetylcholinesterase inhibitors in addition to glucocorticoids 
Guillain-Barre Syndrome
 
 – Plasmapheresis or IVIgG should be considered for subjects with Guillain-Barré syndrome (glucocorticoids are generally ineffective)

Table 2. IBI308 administration adjustments and toxicity management of other potential irAEs

	CTD Grade/Administration Adjustments	Toxicity Management
Any grade	Dose adjustments are not required for AEs unrelated to study treatment or laboratory abnormalities that are not clinically significant (events caused by underlying disease)	Manage based on local clinical practice
Grade 1	No dose adjustments required	
Grade 2	Consider interruption until reduces to grade 0–1 or baseline	
Grade 3	
 • First occurrence: interrupt until reduces to grade 0–1 or baseline • Second occurrence: permanently discontinue • For an AE that reduces to grades 0–2 within 7 days, or grades 0–1 or baseline within 14 days, interrupt and then resume the treatment at the next scheduled date Otherwise, permanently discontinue 	
Grade 4	Permanently discontinue (Note: for grade 4 laboratory abnormalities, the event shall be determined based on clinical signs/symptoms and the clinical judgment of the investigator)	

Table 3. Dose adjustments and toxicity management for infusion reactions

CTD Grade	Administration Adjustments	Toxicity Management
Any grade		
 - Manage based on local clinical practice - Monitor infusion-related reactions (e.g. fever or chills, flushing and/or pruritus, changes in heart rate and blood pressure, dyspnea, chest discomfort, rash, etc.) and allergic reactions (e.g. systemic urticaria, angioedema, asthma, hypotension, tachycardia, etc.)

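### The pre-dose toxicity condition in section 5.3.1 conflicts with Appendix 7 for named events, and grade 3–4 hypothyroidism can be dosed, held or stopped depending on the page used

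*Protocol*

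**What the plan says.** **Condition before each dose.** Protocol 5.3.1 (General principles) reads: "All the toxicities must resolve to NCI CTCAE v4.03 grade 0–1 or baseline levels (excluding alopecia, fatigue, etc". The exception list is open-ended, but it names none of the events below.

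**Appendix 7, Table 1.** The default is to interrupt at grade 2, to interrupt or permanently discontinue at grade 3, and to permanently discontinue at grade 4. Some rows depart from it:
- Thyroid disorders at grade 1–2 and type I diabetes at grade 1–2 need no adjustment. Beside the thyroid row, the management column lists "L-thyroxine replacement therapy or anti-thyroid medications when necessary".
- Hypothyroidism at grade 3 or 4 needs no adjustment.
- Grade 2 dermatitis needs none unless it is refractory beyond 1–2 weeks.
- A line under General Principles states: "For grade 3/4 local inflammation of lesions (such as local pain, irritation, and rash), IBI308 may be continued as determined by the investigator".

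**Appendix 7, Table 2 (other potential irAEs).** At grade 2: "Consider interruption until reduces to grade 0–1 or baseline". The grade 3 cell first asks for recovery to grade 0–1 or baseline after a first occurrence. A later bullet begins "For an AE that reduces to grades 0–2 within 7 days" and allows resumption at the next scheduled date.

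**Table 3 (section 5.3.2).** This covers events the investigator judges related to IBI308. Hypothyroidism has no row. The Other AEs rows interrupt at a first grade 3 event, permanently discontinue at a second, and permanently discontinue at grade 4. Footnote c leaves grade 4 laboratory abnormalities to clinical signs and judgment. Footnote b ties resumption after three endocrine events to control on physiological hormone replacement, not to a grade.

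**Section 4.4.** The lead-in is "Subjects should discontinue treatment/withdrawal from the study in any of the following circumstances". Among the reasons grouped as the investigator's decision is: "A life-threatening event that is treatment-related occurred, regardless of the severity of the event". Item 8 withdraws subjects whose treatment is delayed 6 weeks for adverse reactions and gives no exception.

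**The concern.** A site that applies 5.3.1 as written withholds a dose that the Appendix 7 row for the same event and grade would let it give. For grade 3–4 hypothyroidism a third page, Table 3, leads to interruption or permanent discontinuation.

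Three things are at stake:
- Subjects with the same event can be managed differently at different sites.
- Exposure and counts of discontinuation due to adverse events (SAP 5.6.1) then partly reflect which page was read.
- Protocol 8.4.8 reports subjects who violate the treatment regimen, and the SAP removes major deviations and poor compliance from the per-protocol set. One dose can comply with Appendix 7 and breach 5.3.1, so for these events the deviation count has no single definition.

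**Working it through.** The plan states no figure on this point, so the check sets the rules side by side. It assumes a treatment-related event that is above the subject's own baseline grade, because 5.3.1 accepts baseline level.

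| Event | 5.3.1 | Table 3 | Appendix 7 |
|---|---|---|---|
| Grade 2 thyroid disorder | hold | no row at this grade | no adjustment |
| Grade 2 type I diabetes | hold | no row at this grade | no adjustment |
| Grade 2 dermatitis | hold | no row at this grade | no adjustment until refractory |
| Grade 3 hypothyroidism | hold | Other AEs: interrupt at first, stop at second | no adjustment |
| Grade 4 hypothyroidism | hold | Other AEs: stop, subject to footnote c | no adjustment |
| Resuming after grade 2 hypophysitis or adrenocortical insufficiency | grade 0–1 or baseline | footnote b: controlled on replacement | grade 0–1 or baseline |
| Resuming after grade 3 type I diabetes | grade 0–1 or baseline | footnote b: controlled on replacement | blood glucose controlled |
| Resuming after another grade 3 event | grade 0–1 or baseline | footnote a: grade 0–1 or baseline | two conditions in one cell: grade 0–1 or baseline; grade 0–2 within 7 days |
| Other grade 2 irAE | hold | no row at this grade | interruption to be considered |
| Grade 3/4 local lesion inflammation | hold | not named | continuation permitted |

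**Reading the table.** The first five rows are direct mismatches. Only the two hypothyroidism rows yield all three outcomes. The last two rows are weaker: Appendix 7 permits dosing there but does not require it, so a site that holds satisfies both texts. The lesion line meets 4.4 only if the event is treatment-related and life-threatening.

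**Precedence.** Section 5.4 points to Appendix 7 for irAEs. Section 7.8.1 points to 5.3, 5.4 and Appendix 7 together. Appendix 7 says to use it when the event is an irAE. None of these says what happens when it disagrees with 5.3.1, Table 3 or 4.4.

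**The 6-week rule.** Item 8 of 4.4 has no exception. Section 5.3.2 has two, each allowing resumption after more than 6 weeks once the sponsor's medical manager has been consulted.

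**Size per subject.** Dosing is every 3 weeks.
- Doses due before week 24 (day 169): days 1, 22, 43, 64, 85, 106, 127 and 148, which is 8.
- One held dose: 1/8 = 12.5%.
- A 6-week hold: 6/3 = 2 doses, 2/8 = 25%, leaving 6/8 = 75%.

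SAP 3.2 counts compliance below 80% as poor but gives no formula. If it is doses given over doses planned, and held doses are skipped, one missed dose of eight (7/8 = 87.5%) stays above the limit and two (75%) fall below it. Over a longer course of n planned doses, two missed doses fall below the limit only if (n − 2)/n < 0.80, that is n < 10.

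**Scale of one subject.** The amendment summary reports 28 enrolled, so one reclassified subject is 1/28 = 3.6%.

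**The case against.** **Specific rows qualify a general principle.** Section 5.3.1 is headed as general principles, its exception list is open, and several passages send irAEs to Appendix 7. A sensible site might let the event-specific row govern. That reading is reasonable, but nothing states it. It also does not settle Table 3 against Appendix 7 for hypothyroidism, where both are row-level instructions.

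**No adjustment is not an order to dose.** This is true, and the phrase elsewhere sits beside optional or conditional interruption (grade 1 pneumonitis, grade 2 dermatitis). The page still does not ask for the hold that 5.3.1 requires.

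**The grade 3 cell of Table 2 can be harmonised.** Table 3 uses the 7- and 14-day limits as a test for permanent discontinuation, with resumption at grade 0–1 or baseline. The Table 2 cell may have meant the same. As written it attaches resumption to the limits, so it contains two conditions. It does not plainly direct dosing at grade 2.

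**Stronger readings that the documents do not support.**
- A reader might infer that Appendix 7 continues dosing at grades 2–4 in general. Its default is the reverse.
- A reader might infer that every grade 4 event triggers 4.4, because 7.3 describes grade 4 as "Life-threatening consequences; urgent intervention indicated". That wording applies to terms absent from CTCAE v4.03. Section 7.2 defines life-threatening separately, as immediate risk of death. The 4.4 trigger and the lesion line are both left to the investigator.
- A reader might infer that a prolonged hold under 5.3.1 necessarily ends treatment at 6 weeks. Section 5.3.2 allows exceptions, although 4.4 item 8 does not.
- A reader might infer that a subject stable on thyroid replacement is grade 2. That depends on CTCAE text which the documents do not reproduce.

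**Conclusion.** The inconsistency is real and limited to named events. The unqualified condition in 5.3.1 does not fit the Appendix 7 rows for grade 2 thyroid disorders, grade 2 type I diabetes, grade 2 dermatitis and grade 3–4 hypothyroidism. Table 3 adds a third outcome for hypothyroidism. Footnote b, the grade 3 cell of Appendix 7 Table 2 and the two versions of the 6-week rule are further mismatches. The permissive lines on other grade 2 irAEs and on lesion inflammation are lesser points.

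The number of subjects affected cannot be estimated, because the documents give no rates for these events. The effect on an individual subject's exposure and per-protocol status can be material, given the compliance definition assumed above. Full analysis set membership does not depend on these rules, and nothing here shows a change in ORR. The point deserves correction because it bears on safety management and on how deviations are counted. It takes no position on which clinical rule is right.

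**What to change.** Reconcile section 4.4 (the life-threatening-event reason and item 8), section 5.3.1, Table 3 with its footnotes and the 6-week text below it, and these parts of Appendix 7: the thyroid, type I diabetes, dermatitis, hypopituitarism and adrenocortical insufficiency rows; the lesion-inflammation line; and the grade 2 and grade 3 cells of Table 2. State in one place which text takes precedence when two apply. The sponsor's medical team decides which text stands.

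This can be done in an amendment or clarification letter, with no added visits or tests. If dosing has finished, record the rule used to classify these events before major deviations and per-protocol membership are settled at the data review meeting that precedes database lock.
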